#### WOUND OUTCOMES WITH DIFFERENT THORACOSTOMY CLOSURE TECHNIQUES

Properly closing and stabilizing surgical wound edges to restore their original position is a key consideration in achieving good and satisfactory surgical wound outcomes. Surgical wound complications portend poor immediate outcomes for patients as they require more dressings, may require prolonged antibiotic therapy to manage wound infection, experience more pain, and have a strong potential for prolongation of the length of postoperative hospital stay (24,25). Un-interrupted acute wound healing occurring by first or primary intention as a result of the wound edges being in close proximity to each other, tends to heal with far less inflammatory reaction and granulation tissue

formation and minimal wound contraction (26,27). These inevitably result in earlier wound sealing, lower risk of post-operative contamination and infection as well as satisfactory wound pain control.

Also, considering the long term, the main rationale behind closure of surgical wounds is the achievement of far less scarring that will produce a functional and cosmetic-appealing scar when the wound heals (28). There is growing interest in achieving such scars with rising patients' expectations and in turn, increasing surgeons' awareness of surgical materials and techniques required to close surgical wounds to achieve a scar that is functional and with a satisfactory cosmetic appearance (29). Though, several techniques have been proposed and employed to achieve this kind of closure, there is no stand-out ideal technique because each one is fraught with its own inherent and unique challenges.

The early process of any wound healing by primary intention requires the formation and organization of a thin rim of clot holding together the apposing edges of the wound while the wound progressively gains tensile strength (30). The stability and strength of the wound depends largely on the formation and stability of this clot and the biochemical and mechanical forces within the wound bed. These factors counteract the shearing forces at the wound edges that tend to delay wound sealing which should normally be completed in 2 to 3 days (30,31).

Wound suturing is a time-honored technique of enhancing and improving the chances of a wound sealing at the earliest possible time, that has been practiced by surgeons for many generations. The employment of a suture is to achieve primary closure of wounds irrespective of wound length and topography, by maintaining the wound in apposition while it gains strength during the early phases of wound healing. It also helps with early wound sealing.

Despite these undoubted benefits of wound suturing, there exists some inherent side effects like increased risk of wound infection and wound pain in the early post-operative period and the possibility of suture-related undesired scar outcomes. These benefits are often closely related to the make, design and strength of the suture used as well as the technique of placement and application of the suture in wound closure (30,31). The generally acceptable concept is to use a monofilament and non-absorbable suture of good strength to close superficial wounds to limit the side effects of suture use on early and late wound outcomes (29,30,31,32). This has been corroborated by findings from past and recent human and animal studies (33,34,35). Specifically, using prolene suture, a monofilament and nonabsorbable suture, for superficial wound closure towards achieving good early and late wound outcomes had been identified several years ago and the satisfactory early and late wound outcomes have remained incontrovertible till date (36). Prolene is known to cause minimal tissue reaction, to be associated with minimal wound infection and wound pain while also promoting early wound healing with better cosmetic appearance of the scar (36,37).

For over two decades, to mitigate the effect of suture use whilst encouraging a non-invasive apposition of wound edges, in an attempt to promote early wound sealing and satisfactory wound outcomes; occlusive adhesive dressing have taken a progressive pre-eminence in the early management of surgical wounds as described in some series (38). A dressing is described as occlusive if a moist wound surface is maintained while the dressing is in place (38,39). Occlusive dressings are non-invasive, inhibit water vaporization from wound surface to the atmosphere thereby reducing wound desiccation, encourage early wound epithelialization, improve stability of chronic wound granulation tissue and creates a painless autolysis of any wound necrotic area (39,40). Other additional benefits noted include the protection of the wound bed from environmental contaminants and microorganisms with reduction in risk of wound infection, reduction of wound pain, provision of a cost effective wound care option

by decreasing the nursing time required for wound care and ultimately, the production of a less noticeable scar with far more satisfactory cosmetic outcome (40,41,42).

Several commercially available occlusive dressings are available in clinical practice today. A study has utilized Tegaderm b Pad (3M, Saint Paul, MN) for management of thoracostomy wounds which is applied at the time of chest tube insertion (16). Primapore\* (Smith & Nephew, London, UK) is an economical all-in-one tape and gauze product (43). The peripheral tape at the margin is adhesive while the central guaze is a soft, comfortable, water-resistant, non-adherent island dressing that ensures patient comfort while also serving as an absorbent medium. This is shown in Figures 1 and 2 below.

FIGURE 1: Primapore\* occlusive-adhesive 8.3 x 6cm rectangular dressing

FIGURE 2: Primapore\* occlusive-adhesive dressing applied to a thoracostomy wound

#### CHAPTER THREE

#### METHODOLOGY

#### STUDY DESIGN

The study is a prospective randomized open-label clinical trial comparing the outcomes of an unconventional method of closing thoracostomy wounds after chest tube insertion and removal (Occlusive adhesive-absorbent dressing application i.e. Un-reapproximated wound edges) to a common-place conventional method of closure with purse-string suture (U-suturing or purse-string suturing technique). This design entails random allocation of eligible patients into two groups, namely; Group A (patients who will have purse-string suture placed at the time of insertion of chest tube and who will have this purse-string used for the closure of the thoracostomy wound at the time of chest tube insertion and will have their thoracostomy wound covered with an occlusive adhesive-absorbent dressing at the time of chest tube removal).

#### STUDY AREA AND SITE

The study will be carried out by the principal investigator and his team at the Division of Cardiovascular and Thoracic Surgery of the Department of Surgery at the University College Hospital, Ibadan (UCH). The hospital is an 850-bed tertiary health institution and a regional reference centre for thoracic surgical and advanced pulmonary medical care that serves mainly the states in South-Western Nigeria including Oyo, Ogun, Osun, Ondo and Ekiti states. It also receives referrals for thoracic surgical cases from Lagos and up-country (South-East, South-South and North-Central regions of Nigeria).

These patients seeking thoracic surgical care are often admitted to designated thoracic surgical and Pulmonary medical wards of the hospital via the emergency department or outpatient clinics.

#### STUDY DURATION

The study is expected to span a one (1) year period. It will be conducted on all patients who meet the inclusion criteria that present within the study period.

#### STUDY POPULATION

The study population will be mainly consenting patients who require chest tube insertion for therapeutic purposes and fulfill the inclusion criteria during the study period.

#### SAMPLE SIZE

The sample size will be calculated by comparing the known incidence rate of 6% for acute pneumothorax when a purse- string suture is used and an incidence rate of 1.2% when the wound edges were un-reapproximated since the occurrence of pneumothorax is the most common morbidity or complication that is documented in the literatures (16). Using the software WinPepi (44), 142 subjects grouped into 71 subjects in group A and 71 subjects in group B will be required to compare a proportion rate of 6% in group A and 1.2% in group B, if level of significance is set at 5%, non-response rate set at 5% with the study powered at 80%; for a two-sided test.

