Some commercially available dressings which adhere tightly to the skin and then attach to the drain may also be used but they do not replace the need to stitch the drain firmly in place (10). Another common method is to cover the wound with a water impermeant occlusive dressing material like vaseline gauze or adhesive tape, after removing the chest tubes to prevent air entry into the pleura but the cosmetic result may be unreliable with the wound healing by granulation (11).Petroleum-coated gauze as an occlusive seal was used in the past but it is no longer recommended because it leads to integument breakdown, wound infections, pneumothorax and wound dehiscence (2,7).

Other newer techniques for the management of the chest drain wound after tube removal such as a 2layer method with triclosan-coated sutures have been described(2). This method was designed with lots of advantages such as non-requirement of a stitch removal at follow-up, good wound healing with cosmetically-appealing scars; without an increased risk of infection but it has a drawback of being too expensive with requirement of technical expertise limiting its widespread adoption (2,3).

Sutures may not be necessary, after all, for closure of chest drain site as a study reported very minimal complications when sutures were not used(16). The study showed that the rate of acute pneumothorax after removal was 1.2% as opposed to the documented rate of 6%-10.7% for purse-string sutures. Late pneumothorax rate was 0% and only superficial infections occurred with this method which did not result in empyema thoracis as opposed to the documented rate of 1%-25% for purse-string suture use (16,21,22). There was also a reduction of the cost per patient which was not just from avoiding using a suture but also avoiding the cost of removing such a suture afterwards (16).

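### 71 patients per arm give about 33% power for 6% versus 1.2% acute pneumothorax, not the stated 80%

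*Combined protocol and SAP*

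**What the plan says.** All the inputs stand together in the Sample Size section of Chapter Three. The purse-string arm is given a "known incidence rate of 6% for acute pneumothorax when a purse- string suture is used", and the comparison arm "an incidence rate of 1.2% when the wound edges were un-reapproximated". The remaining settings are a 5% significance level and "non-response rate set at 5% with the study powered at 80%; for a two-sided test". From these, using WinPepi, the section concludes that "142 subjects grouped into 71 subjects in group A and 71 subjects in group B will be required".

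The section on sampling and randomisation repeats the 71 and 71 allocation. The literature review in Chapter Two gives the background to the two rates: "the rate of acute pneumothorax after removal was 1.2% as opposed to the documented rate of 6%-10.7% for purse-string sutures". No other section offers a different basis for the sample size.

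**The concern.** A difference between 6% and 1.2% is 4.8 percentage points between two rare events. With 71 patients per arm that means about four events against one, which is too few for a two-sided 5% test to detect reliably. The stated 80% therefore looked wrong on its face.

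The documents name no primary outcome, and acute pneumothorax is the only outcome with a power justification, so this is the plan's whole case for its size. The study summary says the data will supply a general guideline for managing these wounds and feed an institutional protocol. If the trial finds no significant difference and its report repeats the 80% figure, readers may conclude that the two closure methods carry the same risk of an iatrogenic complication. The data could not support that conclusion.

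**Working it through.** **Inputs (Sample Size section).** p1 = 0.06, p2 = 0.012, difference d = 0.048, two-sided alpha 0.05 (z = 1.960), power 0.80 (z = 0.8416), non-response 5%, two equal arms of 71.

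**Attempt to reproduce 71 per arm.** Pooled-variance formula for two proportions, with mean rate p = (0.06 + 0.012)/2 = 0.036:

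n = [1.960·√(2p(1−p)) + 0.8416·√(p1(1−p1) + p2(1−p2))]² / d²

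- First term: 1.960 × √0.069408 = 0.5164
- Second term: 0.8416 × √0.068256 = 0.2199
- n = 0.7362² / 0.002304 = 235.3, so 236 evaluable per arm
- With continuity correction: (235.3/4) × [1 + √(1 + 4/(235.3 × 0.048))]² = 275.4, so 276 per arm
- After non-response: 236/0.95 gives 249 per arm (498 total); 276/0.95 gives 291 per arm (582 total)

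The plan states 71 per arm (142 total). The required number is about 3.5 times larger (498/142).

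**Other formulas and readings (evaluable per arm for 80% power).**

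| Variant | n per arm |
|---|---|
| Unpooled variance, two-sided | 233 |
| Arcsine, two-sided | 207 |
| One-sided 5%, pooled | 186 |
| One-sided 5%, arcsine | 164 |
| 10.7% vs 1.2%, two-sided | 97 |
| 10.7% vs 1.2%, one-sided | 76 |

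The last two rows use the top of the purse-string range in the literature review instead of the stated 6%. None of the rows reaches 71.

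**Power that 71 per arm gives for 6% vs 1.2%.** Normal approximation: (√71 × 0.048 − 0.5164)/√0.068256 = (0.4045 − 0.5164)/0.2613 = −0.428, and Φ(−0.428) = 0.334. The exact figures come from enumerating the binomial outcomes. About 67 per arm remain after 5% non-response (71 × 0.95 = 67.45).

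| Test, two-sided 5% | 71 evaluable | 67 evaluable |
|---|---|---|
| Normal approximation | 33% | 32% |
| Pearson chi-square, exact power | 32% | 30% |
| Fisher's exact | 13% | 11% |

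**What this means in events.** Expected counts are 71 × 0.06 = 4.3 and 71 × 0.012 = 0.9. Fisher's test needs at least 6 versus 0, or 8 versus 1, to reach significance.

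**Effect for which 71 per arm does give 80% power.** Against 1.2%, the purse-string rate would have to be about 13.3% by the normal approximation (11.9% by exact Pearson, 14.1% by Fisher). For 10.7% versus 1.2%, power at 71 per arm is about 67%.

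**Precision.** At the planned rates, the half-width of the 95% interval for the risk difference is 1.96 × √(0.068256/71) = 0.061. That is 6.1 percentage points, wider than the 4.8-point difference the trial was sized on.

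**The case against.** There are four points to make for the plan.

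- **A possible origin for 142.** A one-sample test of 1.2% against a fixed 6% needs [1.960·√(0.06 × 0.94) + 0.8416·√(0.012 × 0.988)]²/0.048² = 134.7 patients, and 134.7/0.95 = 141.8, which rounds to 142. This may be how the figure arose, but it cannot be proved from the document. It does not rescue the claim, because the section describes a comparison of two randomised arms, and a one-sample total split in half does not give that comparison 80% power. Reading 142 as the number per arm fails too, since power would be 58%.
- **The test.** The Data Analysis section assigns a Cox model to complications and names no test of proportions for them. The 33% and 13% are therefore figures for two-proportion tests and should be labelled so. They match the way the plan itself sizes the trial. A rough events-based calculation for the Cox model (about 5 events, hazard ratio about 0.195) gives about 45%. That figure is unreliable with so few events, and it is still below one half.
- **Scope.** The shortfall is shown for acute pneumothorax only. Other outcomes, such as severe pain, infection or scarring, have no assumed rates, so their power cannot be checked.
- **Equivalence.** The plan states hypotheses of difference and never says that a null result will be read as equivalence. That danger is an inference about readers, and it rests on the 80% figure standing uncorrected.

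These points limit how the finding should be worded. None of them brings 71 per arm near 80% power.

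**Conclusion.** The concern holds. On the plan's own inputs, 80% power needs 236 evaluable patients per arm, and the 71 planned give about one third of the time a significant result on acute pneumothorax, or roughly one time in eight with Fisher's exact test. Allowing for the stated 5% non-response lowers these figures slightly. The conclusion assumes the stated rates of 6% and 1.2%, equal arms and a two-sided 5% test of two proportions. It does not hinge on the choice of formula: power at 71 per arm was below 50% in every variant tried for these rates, including a one-sided test (46%). The stated 80% is a property the design does not have, and it must be corrected.

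**What to change.** Rewrite the Sample Size section, keeping enrolment at 142:

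- State that 71 per arm give about 33% power for 6% versus 1.2% (two-sided 5%, normal approximation), or 13% by Fisher's exact test. Add the figures for 67 evaluable per arm, 32% and 11%.
- State that 80% power applies only to a contrast of about 13% versus 1.2%.

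In the Data Analysis section, add the acute pneumothorax risk difference with its 95% confidence interval, noting the expected half-width of about 6 percentage points. Add one sentence saying that a non-significant result will not be interpreted as showing no difference between the methods.

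The cost is the rewording of one section, one added estimate and one sentence on interpretation, with no extra patients. The price is a much less favourable power statement. If the sponsor wishes to keep the 80% claim for 6% versus 1.2%, the alternative is to re-size to 249 per arm (291 with continuity correction). The document gives no accrual figures from which to judge whether that is feasible in one centre and one year.

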# SAMPLING AND RANDOMISATION TECHNIQUES

A block but balanced randomization technique (Unstratified) will be used in determining the use or otherwise of purse-string in the study population. Randomization and intervention assignment into either of the two groups A or B (purse string versus non-purse string) will be determined by grouping labels (A or B) and serialization generated by the soft-ware Winpepi from number 1 to 142 (i.e. Random assignment of 71 in Group A and 71 in Group B).

The generated sequence will be stored on the computer of a blinded research assistant who will be required to inform the team of the next assigned intervention according to the generated sequence, at the time of chest tube insertion for all included and consenting patients. The research assistant will keep record of all assigned labels and ensure all intervention assignment follows the computer-generated sequence in an uninterrupted and reproducible manner.

# INCLUSION CRITERIA

Patients who are 18 years of age or older who require chest tube insertion for any of the following indications:

- 1. Pleural effusion
- 2. Traumatic or spontaneous pneumothorax
- 3. Traumatic haemothorax
- 4. As an adjunct to a thoracotomy for a non-neoplastic and or non -infective condition

# EXCLUSION CRITERIA

Any patient so described above who has the following will be excluded:

- 1. An associated pyopneumothorax
- 2. Cancer encuirasse of the chest wall
- 3. Unconscious with unclear consent situation
- 4. With infective or neoplastic conditions of the chest wall
- 5. With individual or family history of wound failure e.g. unsightly scars
- 6. Who has had irradiation of the chest or chemotherapy administration within 6 weeks from the time of requirement of the chest tube insertion
- 7. Who is at risk of immunosuppression i.e. diabetes, HIV infection, on steroid therapy, ongoing chemotherapy or who has a congenital or any other acquired immune deficiency state
- 8. Presence of pleural adhesion during the process of chest tube insertion
- 9. Those with chest tube malposition after insertion, confirmed on chest radiograph, who will require tube adjustment

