### SPECIFIC OBJECTIVES

- To compare the tube-related complications of chest tube insertion in patients who have pursestring suture (U-suture placement) at the time of chest tube insertion versus those without pursestring suture placement that are enrolled for Occlusive adhesive-absorbent dressing application at the time of chest tube removal.
- To compare the incidence of early complications after chest tube removal in patients who have purse-string suture re-approximation of thoracostomy wound versus those who have only Occlusive adhesive-absorbent dressing application (Un-reapproximated wound edges)
- To compare the incidence of late wound complication after chest tube removal in patients who have purse-string suture re-approximation of thoracostomy wound versus those who have only Occlusive adhesive-absorbent dressing application (Un-reapproximated wound edges)

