# STUDY VARIABLES AND DEFINITION

The independent variables to be employed for the analysis include:

- Age of the patient
- Sex of the patient
- Presence of specific co-morbidities (Diabetes, Hypertension, Chronic Liver disease, Chronic kidney disease)
- Charleson Comorbidity Index
- History of cigarette smoking and estimated pack years if positive

- Use of steroids and chemotherapeutic agent
- Abnormal Body mass index (Obesity(BMI> 30kg/m^2), Malnutrition(BMI< 18kg/m^2)

The Dependent variables to be employed for the analysis include:

- Presence of severe pain at the chest tube site after chest tube insertion (Average daily pain score after tube insertion > 5 on the Visual Analog Scale and or Numerical Rating Scale)
- Occurrence of tube dislodgement after chest tube insertion
- Occurrence of peri-tubal leakage of fluid after chest tube insertion
- Presence of wound air suck-in after chest tube removal (indicated by presence of air suck-in sound through the wound into the pleural space during quiet and or forced inspiration)
- Occurrence of wound infection after chest tube removal (presence of purulent or offensive wound discharge with or without fever or presence of wound discharge that is microbiologically positive)
- Occurrence of wound dehiscence after chest tube removal
- Occurrence of early (within 7 days) and late pneumothorax (more than 1 week) after chest tube removal confirmed on chest radiography
- Development of raised or elevated thoracostomy wound scars (unsightly scars appearing like hypertrophic scars or keloids) within 3 months of chest tube removal

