The common complications encountered with chest tube insertion are malposition and obstruction, either by occlusion or by kinking; ectopic insertion and tension pneumothorax with significant air leak; hence the need to secure the tube properly (17).Large and medium bore chest drain incisions are usually closed by a suture appropriate for a linear incision(7). Various techniques have been described, but a simple technique of anchoring the tube has not been the subject of a controlled trial (9). A purse string or U-suture placement (horizontal mattress suture) is used to aid removal of the chest drain at a

later date and facilitate closure of the defect on removal of the drain while avoiding the occurrence of an iatrogenic pneumothorax (3,16).

For this technique, the chosen suture should be stout, strong and non-absorbable (silk or prolene) to prevent ease of breakage (7). One or two additional simple or horizontal mattress sutures of generous depth should be placed to properly anchor the tube (7). This suture is also thought to prevent air reentry on drain removal as well as aid in chest drain site healing by apposing the edges of the wound (16). The suture is often tied to close the skin wound snugly around the tube to prevent any peri-tubal leak (4). However, this can result in an unsightly scar and tying this suture and retaining the knot for the purpose of achieving air and water tightness of the incision can worsen the painful experience of patients before and after drain removal. In addition, any delay in tube removal often increases the risk that is inherently associated with the retained suture being a foreign body (16). In other to increase the cosmetic appearance of the scar as well as provide an airtight seal to prevent air re-entry, attempts have been made to place an absorbable suture at the time of drain insertion but such methods may be cumbersome and complicated (16). Some centers have reported significant success with achieving airtightness using single barbed absorbable suture material(15).

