At this stage, for patients in whom a purse-string suture has been assigned to be used (Group A), a size 0 polypropylene suture is used in making the horizontal mattress or U-shaped purse string as illustrated in Figure 3 below.

[figure not shown]

FIGURE 3: Illustration of how the purse-string suture is inserted into the thoracostomy wound

To make this horizontal mattress or U-suture placement or purse-string in the thoracostomy wound, the needle of the suture is inserted from point 1, at 1 cm from the wound edge, through the skin and subcutaneous tissue and then exited through point 2, also 1cm from the wound edge. The needle is then re-inserted through the wound about 2cm along the transverse plane which is point 3. The same motion as performed from point 1 to point 2 is done in a reverse pattern from point 3 to point 4. With this, only the free ends of the suture and the part of the suture between point 2 and point 3 lying on the skin surface will be visible while other parts lie within the thoracostomy wound.

This step of U-suture or purse-string placement will be skipped for all patients assigned to Group B. Thereafter, the blunt dissection is continued with the index finger to the level of the parietal pleura which is breached using the tip of the finger or where the pleural is thickened and fibrotic, with the use of the dissecting forceps. The dissecting finger is introduced into the space to assess for pleural adhesions. As indicated above in the exclusion criteria, all patients with pleural adhesions will be excluded from the study. The intrapleural length of the tube will be estimated from the skin incision to the sternal angle. With the aid of the dissecting forceps, this estimated length of the chest tube with blind-ending external part is then advanced apically and posteriorly into the pleural space.

In both groups, the tube is anchored at the anterior and posterior ends of the wound using size 2 silk sutures placed by narrow horizontal mattress suturing or simple interrupted suturing; to secure the chest tube to the chest wall. For patients in Group A, the placed U-suture or purse-string will be knotted once to create air and water tightness (Figure 4) and the loose ends will also be used to anchor the chest tube by tying the loose ends around the chest for a 2 cm length before making a separate knot on the tube to reinforce the previous silk 2 suture anchorages at both wound ends.

[figure not shown]

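### Exclusions 8 and 9 take effect after the group is known in an open-label trial, and no analysis set keeps those patients in their assigned arm

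*Combined protocol and SAP*

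**What the plan says.** Exclusion Criteria, item 8, reads "Presence of pleural adhesion during the process of chest tube insertion". Item 9 reads "Those with chest tube malposition after insertion, confirmed on chest radiograph, who will require tube adjustment".

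The order of events comes from the procedure text:

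- **Before insertion.** After consent and before the procedure starts, the research assistant is asked for the group (1) Before Chest Tube Insertion). Sampling and Randomisation Techniques agrees: the label goes to the team for patients already included and consenting.
- **During insertion.** The purse-string is placed in Group A and skipped in Group B. Only then is the pleura breached and explored by finger, and at that point "As indicated above in the exclusion criteria, all patients with pleural adhesions will be excluded from the study" (2) During chest tube insertion).
- **Fixation.** Both groups have silk anchors at the two wound ends. In Group A the purse-string is also knotted, and "the loose ends will also be used to anchor the chest tube".
- **After insertion.** A radiograph is taken at once to check tube position (3) Management of indwelling chest tubes).

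Study Design describes the trial as open-label. The first of the Specific Objectives is "To compare the tube-related complications of chest tube insertion in patients who have" a purse-string against those who do not. Study Variables and Definition lists "Occurrence of tube dislodgement after chest tube insertion" as an outcome without defining it; malposition is not listed.

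Data Analysis and Management describes baseline comparisons and an adjusted Cox model, but names no analysis population. Sampling and Randomisation Techniques has the assistant keep a record of all labels.

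On consent, Ethical Consideration has the patient told the group and then asked to complete the form.

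**The concern.** A randomised comparison is protected only if everyone assigned is followed and counted in the assigned group. Here two groups of patients can leave after assignment, on decisions made by people who know the arm. Both decisions involve judgement: whether a finger finds adhesions that matter, and whether a tube's position calls for adjustment.

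The two items differ. Adhesions exist before assignment, so item 8 causes bias only if detection or reporting depends on the known arm. Malposition arises after insertion, when fixation already differs between arms. The literature review states "The common complications encountered with chest tube insertion are malposition and obstruction" and concludes from its list "hence the need to secure the tube properly". Item 9 also has no explicit time limit and dislodgement is undefined, so a tube that has moved could be scored as an outcome or removed as an exclusion.

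Baseline tests and covariate adjustment may show or reduce a measured imbalance, but they do not bring back patients who were dropped. If those patients are not followed, their data cannot be recovered later.

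**Working it through.** **1. Sequence.** Setting the sections side by side:

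| Step | Section | Arm known to team? |
|---|---|---|
| Group requested | 1) Before Chest Tube Insertion | becomes known |
| Purse-string placed (A) or skipped (B) | 2) During chest tube insertion | yes |
| Pleura explored; item 8 applied | 2) During chest tube insertion | yes |
| Tube advanced and anchored; purse-string tied in A | 2) During chest tube insertion | yes |
| Position film; item 9 applied | 3) Management of indwelling chest tubes; Exclusion Criteria | yes |
| Tube removal and post-removal outcomes | 4) Procedure for chest tube removal | yes |

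Both exclusions follow release of the label. Both precede tube removal, so the post-removal outcomes cannot themselves drive them.

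**2. What the plan does with these patients.** No section gives an as-assigned analysis set, or a rule for following, counting or replacing them. The label record would allow a count by arm, but none is required. The proforma records purse-string use (item 31), free-text chest X-ray findings (item 23) and a serial number. The copy read, which is broken in places, shows no dedicated field for adhesions, malposition or reason for exclusion.

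**3. Precision is not the issue.** The documents give no exclusion rate. *Assumed for range only:* 2%, 5% or 10% of 142 excluded is 2.84, 7.10 or 14.20 patients. The average planned pneumothorax rate is (6% + 1.2%)/2 = 3.6%, so these patients carry 0.10, 0.26 or 0.51 expected events.

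Power uses the two-sided 5% pooled normal approximation, Φ[(|p₁−p₂|√n − 1.96√(2p̄(1−p̄))) / √(p₁(1−p₁)+p₂(1−p₂))], with p₁ = 0.06, p₂ = 0.012, p̄ = 0.036:

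- n = 71 per arm: (0.4045 − 0.5164)/0.2613 = −0.428, giving 33.4%
- 2%, 5% or 10% fewer: 32.9%, 32.0% or 30.6%

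The plan states 80% power for 71 per arm. That figure does not reproduce, but this is a separate matter and the present point does not rest on it.

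**4. Effect on a tube-related rate.** No rate is planned for these outcomes. *Assumed for range only:* x of 71 patients in one arm have a complication, and k of those x are excluded from that arm alone. The observed rate goes from x/71 to (x−k)/(71−k).

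| x | x/71 | k = 1 | Fall (points) | k = 3 | Fall (points) |
|---|---|---|---|---|---|
| 4 | 5.63% | 3/70 = 4.29% | 1.3 | 1/68 = 1.47% | 4.2 |
| 7 | 9.86% | 6/70 = 8.57% | 1.3 | 4/68 = 5.88% | 4.0 |
| 14 | 19.72% | 13/70 = 18.57% | 1.1 | 11/68 = 16.18% | 3.5 |

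This is a one-sided worst case by construction. It shows how sensitive an arm of 71 is to a few removals and does not estimate the bias.

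**5. Consent.** Sampling and Randomisation Techniques and 1) Before Chest Tube Insertion put consent before release of the group. Ethical Consideration puts completion of the form after disclosure. The first two agree, so only the third needs rewording.

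**The case against.** The strongest reply concerns item 9. The tube is advanced to an estimated length by the same step in both groups before any anchoring, both groups then receive silk anchors, and the purse-string only reinforces them. The film is immediate, so extra fixation has had little time to act, and malposition on it more naturally reflects where the tube was advanced. Malposition is not a listed outcome, and the scheduled position film suggests that item 9 refers to that first film. This stands. It reduces the arm-dependence of item 9 to a possibility and the overlap with dislodgement to a definition that needs settling. It does not remove the unmasked decision to exclude.

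Item 8 concerns a condition present before assignment, and lung adherence is called a relative contraindication in the introduction, so the exclusion may have a clinical basis. That also stands; the point is who is followed and analysed. Releasing the label after the adhesion check would deal with item 8 more directly, but the described suture step comes before that check, and item 9 would be untouched.

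The consent conflict is a different issue, and a two-stage reading is available: agreement, assignment, then a form authorising the surgeon. The consent form was not available to check. Even so, on that reading the form is completed with the group known, so a patient could decline because of the arm.

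The serial number may already link each proforma to the randomisation list, in which case a new label field is unnecessary.

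**Conclusion.** The concern holds as a defect of the analysis plan. Items 8 and 9 act after the group is known in an open-label trial, and nothing in the documents keeps these patients in an as-assigned analysis. This rests on the text alone and needs no assumption about rates. It should be settled before enrolment.

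A reader might go further and infer that the purse-string prevents malposition, so that item 9 selectively removes tube failures from Group B and biases the tube-related comparison in a known direction. The documents do not support this: they give no malposition rate by arm, both arms have silk anchors, the film is immediate, and malposition is not itself an outcome. Nor do they show that patients have refused, or will refuse, because of their arm.

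Bias is possible, with unknown direction and size. The falls of 1.1 to 1.3 points (one case) and 3.5 to 4.2 points (three cases) depend wholly on the assumed counts and on removal from one arm only.

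**What to change.** **Analysis.** Add to Data Analysis and Management that the main analysis includes every patient whose label was released, in the assigned group, for every outcome that can be assessed. Follow item 8 and item 9 patients on the same schedule where assessable. If no tube is placed, report post-removal outcomes as not assessable, by arm. Report all post-assignment exclusions and losses by arm with reasons. Keep the analysis without item 8 and 9 patients as a sensitivity analysis. Align the wording in Exclusion Criteria and 2) During chest tube insertion.

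**Definitions and records.** State in Study Variables and Definition and in Exclusion Criteria how, and up to what time, a moved tube counts as malposition or as dislodgement. Record adhesions, malposition, reason for exclusion and the assigned label, or state that the serial number links to the label.

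**Consent.** Reword Ethical Consideration to agree with the other two sections, so that the trial consent form is completed before the group is disclosed.

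**Cost.** Wording changes, a few proforma fields, and follow-up of patients who would otherwise be dropped (about 3 to 14 if 2% to 10% of 142, assumed). The downsides are possible dilution of unknown size and some item 8 patients without assessable post-removal outcomes; the sensitivity analysis shows how far the result depends on them. Clinical handling of adhesions and malposition stays with the investigators.
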